#### **3.5 Allocation of Subjects to Competing Studies**

In the event that a study center is participating in similar and competing research studies with the same or similar subject populations, the Investigator must provide documentation to the Sponsor or the Sponsor's authorized designee outlining the methods that the center is using for appropriate subject allocation in order to minimize selection bias.

#### **3.6 Study Schedule of Events**

**Table 2 - Study Event Schedule through PAS Follow-up** presents a schedule of the observations and assessments that have taken or will take place from subject enrollment into the IDE study through the duration of the PAS phase of the study.

# Safety and Effectiveness of the Treatment of Wide Neck, Saccular Intracranial Aneurysms with the Neuroform Atlas™ Stent System

## Short Study Name: ATLAS

**Table 2 - Study Event Schedule through PAS Follow-up**

	ATLAS IDE Event Schedule						ATLAS PAS Event Schedule £		
	Pre-Implant	Implant / Procedural	Post-Implant †	2 Months (60d) ± 1 month	6 Months (180d) ± 1 month	12 Months (365d) ± 2 months	2 Years (730d) ± 6 months	3 Years (1095d) ± 6 months	Post 3-Years (43 – 60 months) ††
Medical History	X								
Neurological Exam*	X					X	X ∞	X ∞	X ∞
mRS†	X		X	X	X	X	X ∞	X ∞	X ∞
NIHSS*/**	X			±/-**	±/-**	X	X ∞	X ∞	X ∞
Hunt and Hess*/***	X		X			X	X ∞	X ∞	X ∞
Angiography****	X **** (MRA, CTA or DSA)	X (DSA)		+/-**** (MRA or DSA, per institution standards)	+/-**** (MRA or DSA, per institution standards)	X (DSA)	+/-**** (MRA, CTA, or DSA, per institution standards)	+/-**** (MRA, CTA, or DSA, per institution standards)	+/-**** (MRA, CTA, or DSA, per institution standards)
Adverse Event	X	X	X	X	X	X	X ∞	X ∞	X ∞
Antiplatelet	X		X	X	X	X	X	X	X
Quality of Life	X					X			

† Assessments must be performed within 72 hours after implant procedures, and prior to hospital discharge.

†† Post 3-year visits are required only for those subjects whose index procedure took place ≥ 43 months and ≤ 60 months prior to their enrollment into the PAS phase of the study.

\* At each Clinical Trial Site, a non-treating physician (or an appropriately trained/qualified designee) will be responsible for performing neurological examinations and/or performing assessments using neurologic rating/grading scales (mRS, NIHSS, Hunt and Hess). In addition, a neurological examination and/or an assessment using a neurologic rating/grading scale may be performed at any point in time if it is appropriate to do so, or in the case of a new neurological event.

\*\* The NIHSS is required at baseline and at 12 months of follow-up. In addition, the NIHSS is required at the 2- and 6-month follow-up visit and at any unscheduled visit if the subject's mRS score is > 0 in association with an adverse neurological event.

\*\*\* Hunt and Hess scoring will be performed only when evaluating subjects who have evidence of subarachnoid hemorrhage.

\*\*\*\* Pre-implant angiography (MRA, CTA, or DSA) may be performed up to 6 months prior to treatment. In addition to the post-implant and 12 month angiographic studies, it is recommended that an imaging study be performed within 24 hours of the onset of symptoms in any treated subject suspected of having a stroke. Although not required, if it is standard of care to do so at a given Clinical Trial Site, imaging (MRA or DSA) may be performed at the 2- or 6-month follow-up visit or per standard of care at each institution for the 2 and 3 years long term follow up visit.

∞ At 2-year, 3-year, and post 3-year follow-up, NIHSS, mRS and neurological exams will be collected if performed. For any suspected stroke events that occur in the PAS, NIHSS will be collected at the time of event and at 24 hours post event; mRS will be collected at discharge from event and at a minimum of 90 days post event. For any aneurysm rupture case, Hunt and Hess grade will be performed or collected if available. Any imaging performed due to suspected stroke event will be submitted to the sponsor. AEs can be collected via retrospective chart review, phone calls or in-person visits and will include all the new and ongoing adverse events.

£ At least one (1) ATLAS PAS visit will be conducted in-person.

**STRYKER CONFIDENTIAL - THIS DOCUMENT CONTAINS CONFIDENTIAL AND PROPRIETARY INFORMATION THAT IS THE PROPERTY OF STRYKER CORPORATION. NEITHER THIS DOCUMENT NOR THE INFORMATION HEREIN MAY BE REPRODUCED, USED, OR DISCLOSED TO ANY THIRD PARTY WITHOUT THE PRIOR WRITTEN CONSENT OF STRYKER CORPORATION.**

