#### **2.4.1.2 Primary Safety Endpoint**

The primary safety endpoint is:

Any major ipsilateral stroke or neurological death within 12 months.

An ipsilateral stroke will be defined as an acute episode of focal or global neurological dysfunction due to brain or retinal infarction, or due to an intracranial hemorrhage inclusive of subarachnoid, intraventricular or intraparenchymal hemorrhage, occurring in the same hemisphere as the target aneurysm.

A major ipsilateral stroke will be defined as an ipsilateral stroke that is associated with an increase of 4 or more points on the NIHSS at 24 hours after symptoms onset.

Note: For the purpose of consistency with the primary endpoint definition, strokes in the posterior circulation adjudicated as being strokes “within the treated vascular territory” will be called “ipsilateral” strokes.

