### **3.11 Unscheduled Visits**

Imaging performed in response to an adverse event will be documented in the case report forms. These images will be shared with the Imaging Core Lab, and copies of the images will be provided to the Sponsor so that CEC review and event adjudication can be facilitated. If a subject is suspected of having a stroke, it is recommended that an imaging study be performed within 24 hours of the onset of symptoms in order to confirm, and to evaluate whether the stroke is/was ischemic or hemorrhagic in nature. In addition, a neurological examination and/or an assessment using neurologic rating/grading scales (mRS, NIHSS, Hunt and Hess) should be performed as required in order to determine the severity of the stroke.

If a subject presents with an adverse event, he/she will receive appropriate treatment per site standard of care. If the subject's condition precludes him/her from undergoing angiography or any other evaluation specified in the protocol, the Investigator should document whether a stable clinical endpoint has been reached, or whether the subject's status is associated with an adverse event possibly related to the device or procedure. All efforts will be made to retain the subject for safety follow up. If the subject is withdrawn from the study, reasons for the subject's inability to continue with study evaluations will be documented.

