### **IPSILATERAL STROKE**

An acute episode of focal or global neurological dysfunction due to brain or retinal infarction, or from an intracranial hemorrhage (inclusive of subarachnoid, intraventricular or intraparenchymal hemorrhages) in the same hemisphere of the target aneurysm. A major ipsilateral stroke is an ipsilateral stroke which is associated with an increase of 4 or more points on the NIHSS at 24 hours after stroke onset.

Note: For the purpose of consistency with the primary endpoint definition, strokes in the posterior circulation adjudicated as being strokes “within the treated vascular territory” will be called “ipsilateral” strokes.

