### **STROKE**

A neurological deficit lasting 24 hours or longer. The stroke shall be based on clinical presentation and imaging studies shall be utilized to discern between ischemic versus hemorrhagic origin. The 24-hour criterion is excluded if the subject undergoes cerebrovascular surgery or dies during the first 24 hours. The definition includes subjects presenting with clinical signs and symptoms suggestive of subarachnoid hemorrhage, intracerebral hemorrhage, or cerebral infarction. The definition also includes sudden loss or worsening of visual acuity due to retinal artery occlusion or retinal emboli. The definition excludes slowly progressive cranial nerve palsies or progressive visual field deficits due to continued aneurysm growth. The definition also excludes stroke events in cases of blood disorders such as leukemia or external events such as trauma.

Strokes will be categorized as ipsilateral or contralateral and periprocedural (less than or equal to 30 days) or late (greater than 30-days from the procedure). A stroke with clinical symptoms that resolves within 24 hours but with a brain imaging study showing infarction of vascular origin will be considered a minor stroke. Stroke severity will be graded by the Investigator as major or minor based on the definitions below:

- **Permanent:** A new neurological deficit which does not resolve completely during the period of observation
- **Transient:** A new neurological deficit which resolves completely during the period of observation
- **Major Stroke:** A stroke which is associated with an increase in the NIH Stroke Scale by  $\geq 4$
- **Minor Stroke:** A stroke which is associated with an increase in the NIH Stroke Scale by  $< 4$

---

**Safety and Effectiveness of the Treatment of Wide Neck, Saccular Intracranial Aneurysms with the Neuroform Atlas™ Stent System**

---

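### Major stroke is defined by the NIHSS 24 hours after onset, but the 12-month IDE phase never requires a score at that time, so some strokes could be mis-graded.

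*Combined protocol and SAP*

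**What the plan says.** The primary safety endpoint is "Any major ipsilateral stroke or neurological death within 12 months". Section 2.4.1.2 defines a major ipsilateral stroke as "an ipsilateral stroke that is associated with an increase of 4 or more points on the NIHSS at 24 hours after symptoms onset". The Ipsilateral Stroke entry in Appendix B gives the same rule: "an increase of 4 or more points on the NIHSS at 24 hours after stroke onset".

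The IDE-phase provisions for collecting the NIHSS are these:

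- **Table 2, NIHSS footnote:** "The NIHSS is required at baseline and at 12 months of follow-up". The next sentence adds the 2-month, 6-month and unscheduled visits, on condition that mRS is above 0 and linked to a neurological adverse event.
- **Table 2, implant and post-implant columns, and section 3.9.2:** no NIHSS. The assessments before discharge and within 72 hours are mRS and, for some subjects, Hunt and Hess, plus adverse events.
- **Table 2, footnote on assessors:** a rating scale may be used when a new neurological event occurs.
- **Section 3.11, suspected stroke:** an examination and/or a scale (mRS, NIHSS or Hunt and Hess) "should be performed as required in order to determine the severity of the stroke". The only 24-hour statement there concerns imaging, and it is a recommendation.

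For suspected strokes in the post-approval study (PAS), a further Table 2 footnote says "NIHSS will be collected at the time of event and at 24 hours post event". Sections 4.6 and 4.8 call the long-term analysis descriptive, with no formal hypotheses.

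The general Stroke entry in Appendix B defines a major stroke by a rise of 4 or more with no time point, and states "Stroke severity will be graded by the Investigator as major or minor based on the definitions below". Section 2.8 assigns the primary safety endpoint to an independent Clinical Events Committee (CEC), and section 10.2 says the adjudicated data are used in the final analysis.

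**The concern.** The stroke half of the endpoint depends on one measurement at one time. A site could follow the IDE schedule exactly and still not have it. The sponsor wrote the needed rule, but only for the phase after the endpoint has been tested.

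The exposed case is a stroke around the procedure. If the first NIHSS comes weeks later, after partial recovery, a rise of 4 or more at 24 hours may have shrunk below 4. The stroke could then be graded minor, or left without a grade. Adjudicators can use only what was recorded.

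The success rule compares an upper confidence limit with 20% (anterior) or 25% (posterior). Any net loss of true events from the numerator would raise the chance of passing when the true rate is at or near the goal.

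**Working it through.** **1. Follow one case through the schedule.** Take a stroke on the day of implant.

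| Time | What the IDE phase requires | Gives the 24-hour NIHSS? |
|---|---|---|
| Before implant | NIHSS | No, but supplies the reference value |
| At the event | Examination and/or a scale, untimed (section 3.11) | Only if the site chooses it |
| Before discharge, within 72 hours | mRS; Hunt and Hess for some | No |
| 2 months ± 1 month | NIHSS only if mRS > 0 with a neurological event | No |
| 6 months ± 1 month | Same condition | No |
| 12 months ± 2 months | NIHSS | No |

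The first scheduled NIHSS opportunity is thus one to three months after implant (2 ± 1), and it lapses if mRS has returned to 0. A stroke after discharge may lead to an unscheduled visit, but that score is tied to the visit and to mRS, not to onset.

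**2. Reproduce the plan's safety power.** Inputs are n = 153 evaluable per cohort, planning rates of 8% and 12%, goals of 20% and 25% (section 4.2), and the two-sided 95% Clopper-Pearson interval (section 4.6).

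- Upper limit for x events: U(x) = the 0.975 quantile of Beta(x + 1, n − x).
- Passing count c: the largest x with U(x) below the goal.
- P(pass) = P(X ≤ c), with X ~ Binomial(153, p).

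Anterior: U(20) = 19.46% and U(21) = 20.21%, so c = 20. P(X ≤ 20) at p = 0.08 is 98.9%.

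Posterior: U(27) = 24.63% and U(28) = 25.35%, so c = 27. P(X ≤ 27) at p = 0.12 is 98.5%.

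Both agree with the stated figure of approximately 99%.

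**3. Illustrate the effect of missed events.** Let m be the share of true endpoint events not graded as major, so the observed rate is p(1 − m). The documents give no value for m; those below are assumptions. With the true rate at the goal:

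| m | Anterior observed rate | P(pass) | Posterior observed rate | P(pass) |
|---|---|---|---|---|
| 0% | 20% | 1.7% | 25% | 2.0% |
| 5% | 0.20 × 0.95 = 19% | 3.4% | 0.25 × 0.95 = 23.75% | 4.3% |
| 10% | 0.20 × 0.90 = 18% | 6.5% | 0.25 × 0.90 = 22.5% | 8.7% |
| 30% | 0.20 × 0.70 = 14% | 42.6% | 0.25 × 0.70 = 17.5% | 57.0% |

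At m = 5%, both cohorts already exceed the 2.5% one-sided error that a two-sided 95% interval implies.

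With the true rate at the planning value, m = 30% moves P(pass) from 98.9% to 99.99% (anterior) and from 98.5% to 99.99% (posterior).

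Two limits apply. The calculation shrinks the whole composite, although neurological death needs no NIHSS, so each increase is an upper estimate for its m. It also fixes the posterior cohort at 153, although that cohort's adaptive design may stop enrolment earlier.

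**The case against.** The strongest reply is that stroke assessment is not absent. mRS and adverse events are recorded for every treated subject before discharge, section 3.11 asks for an assessment of severity, and the conditional footnote requires some NIHSS scores between baseline and 12 months. An in-hospital stroke should therefore be detected. That stands: the gap is an untimed score for grading, not a failure to detect strokes.

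Second, the CEC adjudicates, and its charter may say how to grade an event without a 24-hour score. That is possible and cannot be checked here. The protocol itself states no such rule, and a charter cannot supply a score that was never taken.

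Third, a reader might infer that the bias must run toward passing. The documents do not support that. A score taken before 24 hours, or after a later worsening, could over-grade. Under-grading is the more plausible direction only because the scheduled scores fall late.

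Fourth, a reader might infer that the untimed Appendix B definition governs the secondary safety endpoint, because section 2.4.2.2 refers to the Appendices. That endpoint concerns major ipsilateral stroke, and the Ipsilateral Stroke entry carries the 24-hour rule. An untimed rise of 4 or more is also broader than a timed one, so it does not by itself imply under-counting. What remains is two entries to reconcile.

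**Conclusion.** The concern holds as a gap between the endpoint definition and the data the IDE phase requires. The definition needs a 24-hour NIHSS, no IDE-phase provision requires one, and the only rule that does so applies after the tested period. The plan's safety power reproduces and is not in question.

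The size of any effect cannot be derived from the documents. Under assumed losses of 5% to 30%, and with the true rate at the goal, the chance of a wrong pass is 3.4% to 42.6% (anterior) and 4.3% to 57.0% (posterior), against 1.7% and 2.0% with complete grading. These are upper estimates that treat the whole composite as NIHSS-dependent. At the planning rates the conclusion would hardly change. The gap matters if the device is less safe than planned, which is the case the goals exist to detect.

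A reader might go further and conclude that the anterior result is unsound. The documents do not show that: they do not say how many strokes lacked a 24-hour score or how the CEC treated them.

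**What to change.** 1. **Measurement.** Extend the PAS footnote rule to the IDE phase in Table 2 and section 3.11: for every suspected stroke from the index procedure through 12 months, record the NIHSS at the event and at 24 hours. This can help only subjects still in IDE follow-up, in practice the posterior cohort. It cannot create scores for anterior subjects, whose indication was approved in May 2019.
2. **Analysis, both cohorts.** Report how many strokes lack a 24-hour score. Add a sensitivity analysis that counts ipsilateral strokes without that score as major unless the records show a rise below 4. This should stay a sensitivity analysis: as a primary rule it is debatable, and for the anterior cohort it would be set after the fact.
3. **Definitions.** Reconcile the untimed, Investigator-graded major stroke wording in the Appendix B Stroke entry with section 2.4.1.2, the Ipsilateral Stroke entry, and the CEC's role in section 2.8. If the charter already has a rule for missing 24-hour scores, cite it in the protocol.

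The cost is a short bedside score for the few subjects with a suspected stroke, a count and one added analysis, and some wording. The observed event rate may come out higher. No sample size or power figure changes.

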# **Safety and Effectiveness of the Treatment of Wide Neck, Saccular Intracranial Aneurysms with the Neuroform Atlas™ Stent System**

## **Short Study Name: ATLAS**

### **3.7 Pre-implant**

#### **3.7.1 Baseline Evaluation**

Once the Site Investigator has verified that the subject meets all of the study eligibility criteria, and once the subject has signed the informed consent, the subject will undergo a baseline evaluation. This will consist of the following assessments and/or procedures as performed on all subjects prior to implant:

- Medical history
- Neurological examination (including global neurological assessments and evaluation for cranial nerve deficits)

*NOTE: If visual field abnormalities are evident upon examination, a formal ophthalmology consult with visual field analysis should be obtained.*
- Neurologic rating/grading scales including the following:
  - mRS (all subjects)
  - NIHSS (all subjects)
  - Hunt and Hess (for subjects with a ruptured aneurysm and evidence of subarachnoid hemorrhage)
- Angiography (DSA, CTA, or MRA; may be performed up to 6 months prior to treatment)
- Quality of Life (QoL) assessment

QoL data will be collected using the EQ-5D-3L™ system, a generic, standardized, validated  measure of health status consisting of two parts:

#### **Descriptive System**

- Consists of 5 dimensions (5D) including mobility, self-care, usual activities, pain/discomfort, and anxiety/depression
- Subjects rate each dimension using 3 levels (3L) including no problems, some problems, and extreme problems

#### **Visual Analogue System (VAS)**

- Presented in a thermometer-like fashion
- Records the self-rated health of a subject on a scale of 0-100 (worst to best imaginable health state)

#### **3.7.2 Pre-Implant Pharmacotherapy**

The following standard antiplatelet regimen is recommended for pre-implant use in enrolled subjects with unruptured aneurysms in accordance with routine clinical practice. Substitutions for these medications are allowed at the discretion of the Investigator as long as the antiplatelet efficacies are equivalent. Do not use the Neuroform Atlas™ Stent System or embolic coils in subjects in whom antiplatelet therapy is contraindicated.

# **Safety and Effectiveness of the Treatment of Wide Neck, Saccular Intracranial Aneurysms with the Neuroform Atlas™ Stent System**

## **Short Study Name: ATLAS**

### **Recommended Dosage:**

- Aspirin (ASA) 75 or 81 mg (minimum dose) to 325 mg (maximum dose) PO q.d. for at least 5 days prior to the implant procedure
- Clopidogrel/Plavix 75 mg PO q.d. for at least 5 days prior to the implant procedure

## **3.8 Implant**

### **3.8.1 Implant/Procedural Pharmacotherapy**

All procedures will be performed under general anesthesia. Subjects will be anticoagulated during the implant procedure. Anticoagulation will be managed in accordance with site standard of care.

### **3.8.2 Implant/Procedural Steps**

As previously indicated, the Neuroform Atlas™ Stent System consists of a laser cut, nitinol, self-expanding stent preloaded over a delivery wire inside an introducer sheath. The Neuroform Atlas™ Stent System is shipped with detailed written Directions for Use (DFU). Prior to enrolling and treating a subject in the study, all Investigators will review and understand the DFU, and will be trained by the Sponsor with regards to use of the Neuroform Atlas™ Stent System.

1. Select an appropriate stent diameter based on reference vessel diameter, and select a stent length that is at least 8mm longer than the width of the aneurysm neck (in order to maintain a minimum of 4mm of stent length along the parent vessel on either side of the aneurysm neck). Refer to **Section 8, Device Description**, for additional stent sizing recommendations.
2. Follow the procedure outlined in the DFU regarding preparation, positioning and deployment of the Neuroform Atlas™ Stent System. In summary, these steps are as follows:
  - The sheath and delivery wire are used to transfer the Neuroform Atlas™ stent into a 0.0165" - 0.0170" ID microcatheter
  - After transfer, the sheath is removed from the proximal end of the delivery wire
  - The delivery wire is then used to advance the stent to the distal end of the microcatheter
  - The microcatheter, stent, and delivery wire are repositioned as a unit in order to ensure that the stent is located across the aneurysm
  - The stent is deployed across the neck of the aneurysm by stabilizing the delivery wire and withdrawing the catheter
3. The beginning of the procedure will be defined as the point in time when the first puncture or incision is made. The end of the procedure will be defined as the point in time when wound closure is complete. If these start and stop times are not documented in the nursing or anesthesia records, the time stamp of the initial procedural angiogram and final procedural angiogram will be used.

The following types of information will be collected regarding the implant procedure:

- Date of admission
- Procedure date, time, clinical site, investigator performing procedure
- Duration of procedure
- Device information
  - Neuroform Atlas™ Stent
  - Coil type used – brand/model
  - Adjunctive device use (e.g., balloon)
- Technical success of stent assisted coiling procedure
- Intra-operative AEs

